## **2. STUDY OBJECTIVES AND ENDPOINTS**

[figure not shown]
### **2.1. Study Objectives**

#### **2.1.1. Primary Objectives**

- Part 1: To evaluate the safety and tolerability of INCB050465 in combination with ruxolitinib in subjects with MF (PMF, PPV-MF, or PET-MF) and select a dose for further evaluation.
- Parts 2, 3, and 4: To evaluate the efficacy of INCB050465 in combination with ruxolitinib on spleen volume reduction in subjects with PMF, PPV-MF, or PET-MF.

#### **2.1.2. Secondary Objectives**

- To evaluate the efficacy of INCB050465 in combination with ruxolitinib on subject reports of MF symptoms.
- To evaluate the efficacy of INCB050465 in combination with ruxolitinib on response using International Working Group (IWG)–Myeloproliferative Neoplasms Research and Treatment (MRT) criteria.
- To assess the PK of INCB050465 and ruxolitinib alone and when given in combination in subjects with MF.
- To evaluate the safety and tolerability of INCB050465 when combined with ruxolitinib in subjects with MF.

## **2.2. Study Endpoints**

### **2.2.1. Primary Endpoints**

- Part 1: Determination of the doses of INCB050465 that are safe and tolerable in combination with ruxolitinib.
- Parts 2, 3, and 4: Change and percentage change in spleen volume from baseline through Week 12 as measured by magnetic resonance imaging (MRI; or computed tomography [CT] scan in applicable subjects).

### **2.2.2. Secondary Endpoints**

- Change and percentage change in spleen volume from baseline through Week 24 as measured by MRI (or CT scan in applicable subjects).
- Change and percentage change in total symptom score from baseline through Week 12 or Week 24 as measured by the Myelofibrosis Symptom Assessment Form version 3.0 (MFSAF v3.0) symptom diary and by the Myeloproliferative Neoplasms Symptom Assessment Form (MPN-SAF).
- Number of subjects with responses according to the 2013 IWG consensus criteria for treatment response in PMF, PPV-MF, and PET-MF.
- Patient Global Impression of Change score at each visit where the variable is measured.
- Population PK parameters of INCB050465 and ruxolitinib alone and in combination (eg, AUC, Cmax) will be summarized.
- Safety and tolerability of the treatment regimens through assessment of AEs and changes in safety assessments including laboratory parameters.

### **3. SUBJECT ELIGIBILITY**

Deviations from eligibility criteria are not allowed because they can potentially jeopardize the scientific integrity of the study, regulatory acceptability, and/or subject safety. Therefore, adherence to the criteria as specified in the Protocol is essential.

#### **3.1. Study Population**

Male or female individuals subjects aged 18 years or older who have been diagnosed with PMF or secondary MF (PPV-MF or PET-MF) and who have a suboptimal response while receiving ruxolitinib monotherapy for a period of at least 6 months, with a stable ruxolitinib dose regimen for at least 8 weeks before the first administration of INCB050465.

#### **3.2. Subject Inclusion Criteria**

A subject who meets all of the following criteria may be included in the study:

1. Men and women aged 18 years or older.
2. Diagnosis of PMF, PPV-MF, or PET-MF.
3. Treated with ruxolitinib for  $\geq$  6 months with a stable dose for  $\geq$  8 weeks (acceptable doses are 5 mg BID to 25 mg BID).
4. Evidence of inadequate response to ruxolitinib:
  - a. Palpable spleen of  $>$  10 cm below the left subcostal margin on physical examination at the screening visit OR
  - b. Palpable splenomegaly of 5 to 10 cm below left subcostal margin on physical exam AND active symptoms of MF at the screening visit as demonstrated by presence of 1 symptom score  $\geq$  5 or 2 symptom scores  $\geq$  3 using the Screening Symptom Form ([Appendix D](#)).
5. Subjects with an ECOG performance status of 0, 1, or 2 (see [Appendix G](#)).
6. Screening bone marrow biopsy specimen available or willingness to undergo a bone marrow biopsy at screening/baseline; willingness to undergo bone marrow biopsy at Week 24.
7. Life expectancy of at least 24 weeks.
8. Willingness to avoid pregnancy or fathering children based on the criteria below:
  - a. Woman of nonchildbearing potential (ie, surgically sterile with a hysterectomy and/or bilateral oophorectomy OR  $\geq$  12 months of amenorrhea and at least 50 years of age).
  - b. Woman of childbearing potential who has a negative serum pregnancy test at screening and before the first dose on Day 1 and who agrees to take appropriate precautions to avoid pregnancy (with at least 99% certainty) from screening through safety follow-up. Permitted methods that are at least 99% effective in preventing pregnancy (see [Appendix A](#)) should be communicated to the subject and their understanding confirmed.

- c. Man who agrees to take appropriate precautions to avoid fathering children (with at least 99% certainty) from screening through 93 days after treatment with INCB050465. Permitted methods that are at least 99% effective in preventing pregnancy (see [Appendix A](#)) should be communicated to the subject and their understanding confirmed.

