### **1.7. Justification of Study Treatment Regimen**

In clinical studies to date, DLTs have not been observed at doses of INCB050465 up to 20 mg, and target inhibition as assessed by phosphorylated protein kinase B levels in peripheral blood showed > 80% inhibition at trough in subjects receiving 5 mg, 10 mg, 15 mg, or 20 mg of INCB050465. Exploration of doses of 5, 10, 20, or 30 mg in the present study is therefore clinically reasonable. Indeed, doses of 10 or 20 mg given daily for 8 weeks followed by weekly have been well tolerated, and no DLTs were observed.

Previously, Part 3 was implemented to explore daily doses beyond Week 8. The 8-week higher dose was retained, and subjects in Part 3 either switched to weekly dosing or remained on daily doses but at a lower dose. Part 4 will use all daily dose regimens and will directly examine the

role a higher initial dose might play in overall response and duration of response. From the subject's perspective, taking the same dose every day from start to finish would be the simplest regimen to follow. However, the initial use of a higher dose might be critical to achieve significant decreases in spleen size and/or symptom scores more quickly in this refractory population. Part 4 of the study will compare a group of subjects who begin receiving INCB050465 at 20 mg QD, then decrease to 5 mg QD after 8 weeks (dose group TG5I/M) with a group who begin at and remain on doses of 5 mg QD (dose group TG5D).

All parts of the study require that subjects be on a stable dose of ruxolitinib for at least 8 weeks before the screening visit; doses of ruxolitinib may not exceed 25 mg BID for subjects with platelet counts  $\geq 100 \times 10^9/L$  and may not exceed 10 mg BID for subjects with platelet count  $\geq 50 \times 10^9/L$  but  $< 100 \times 10^9/L$ , which mirrors the recommendations for treatment doses in the ruxolitinib complete prescribing information. The requirement for a stable dose before study entry further implies adequate tolerability for the dose of ruxolitinib in a given subject.

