### **3.3. Subject Exclusion Criteria**

A subject who meets any of the following criteria will be excluded from the study:

1. Use of experimental drug therapy for MF or any other standard drug (eg, danazol, hydroxyurea, etc.), with the exception of ruxolitinib within 6 months of starting study (combination) therapy and/or lack of recovery from all toxicities from previous therapy (except ruxolitinib) to Grade 1 or better.
2. Inability to swallow food or any condition of the upper gastrointestinal tract that precludes administration of oral medications.
3. Unwillingness to be transfused with blood components.
4. Recent history of inadequate bone marrow reserve as demonstrated by the following:
  - a. Platelet count  $< 50 \times 10^9/\text{L}$  in the 4 weeks before screening or platelet transfusion(s) within 8 weeks before screening.
  - b. Absolute neutrophil count (ANC) levels  $< 0.5 \times 10^9/\text{L}$  in the 4 weeks before screening.
  - c. Subjects with peripheral blood blast count of  $> 10\%$  at the screening or baseline hematology assessments.
  - d. Subjects who are not willing to receive RBC transfusions to treat low hemoglobin levels.
5. Inadequate liver function at screening visit as demonstrated by the following:
  - a. Direct bilirubin  $\geq 2.0 \times$  the upper limit of laboratory normal (ULN). (NOTE: direct bilirubin will only be determined if total bilirubin is  $\geq 2.0 \times$  ULN).
  - b. ALT or AST  $> 2.5 \times$  ULN.
6. Inadequate renal function at screening visit as demonstrated by creatinine clearance  $< 50 \text{ mL/min}$  measured or calculated by Cockcroft-Gault equation, or glomerular filtration rate  $< 50 \text{ mL/min}/1.73 \text{ m}^2$  as calculated using the Modification of Diet in Renal Disease formula.
7. Active bacterial, fungal, parasitic, or viral infection that requires therapy. Subjects with acute infections requiring treatment should delay screening/enrollment until the course of therapy has been completed and the event is considered resolved. Prophylactic antibiotics will be permitted.
8. Active hepatitis B virus (HBV) or hepatitis C virus (HCV) infection that requires treatment or at risk for HBV reactivation. Hepatitis B virus DNA and HCV RNA must be undetectable upon testing. At risk for HBV reactivation is defined as hepatitis B surface antigen positive or anti-hepatitis B core antibody positive. Cytomegalovirus must be undetectable by polymerase chain reaction.

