## 4. INVESTIGATIONAL PLAN

### 4.1. Overall Study Design

This is a Phase 2 study of the combination of the PI3K $\delta$  inhibitor INCB050465 and the JAK 1/2 inhibitor ruxolitinib in subjects with PMF or secondary MF (PPV-MF or PET-MF) who have suboptimal response while receiving ruxolitinib monotherapy. Suboptimal response is based on assessment of suboptimal reductions in spleen size or symptoms and is defined in the inclusion criteria (Section 3.2). At least 6 months of prior ruxolitinib therapy is required, including ruxolitinib administration at a stable dose for at least 8 weeks before randomization. The study is composed of 4 parts:

**Part 1** was an open-label safety run-in portion designed to assess the safety and tolerability of the combination of INCB050465 with ruxolitinib and to select appropriate doses of INCB050465 for Part 2 in this patient population. Part 1 has been completed.

**Part 2** was planned to be a block-randomized open-label study with 2 treatment groups: TG10 and TG20. Both treatment groups use daily doses for the first 8 weeks, then weekly doses at the same strength through EOT. Enrollment in Part 2 was suspended with implementation of Amendment 5.

**Part 3** was planned to be an open-label study to compare daily versus weekly long-term doses. All subjects would begin with INCB050465 20 mg QD. After 8 weeks, subjects in TG5 would continue receiving INCB050465 at 5 mg QD, and subjects in TG20 would continue receiving INCB050465 at 20 mg once weekly. Enrollment in Part 3 will be suspended with implementation of Amendment 6.

**With Amendment 6, Part 4** is added to directly compare different daily dosing regimens and the impact of an initial higher dose of INCB050465 on long-term response. Subjects in Part 4 will be randomized to 1 of 2 groups: TG5D will begin on Day 1 with a daily dose of 5 mg, and subjects will continue receiving 5 mg QD indefinitely or until discontinuation criteria are met; TG5I/M will begin on Day 1 with a daily dose of 20 mg (the induction dose), and after 8 weeks subjects will switch to 5 mg QD (the maintenance dose). Treatment for subjects randomized to TG5I/M will continue indefinitely or until discontinuation criteria are met.

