### **5.3.2. Ruxolitinib**

#### **5.3.2.1. Description and Administration**

Ruxolitinib will be self-administered as a BID oral treatment using the dose designated as the stable dose at the time of the screening visit for each subject. Acceptable doses are 5 mg BID to 25 mg BID.

Doses of ruxolitinib should be self-administered approximately 12 hours apart without regard to food.

Note that subjects must be instructed to withhold the morning dose or ruxolitinib until reaching the clinic for each study visit where administration will occur. The dose may need to be reduced or interrupted for declining platelet count or ANC as described in Section 5.5 and will be increased or restarted with recovery of hematologic parameters.

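### Section 1.7 sets a platelet-dependent ruxolitinib ceiling for all parts that the eligibility and dosing text for Parts 2 to 4 does not carry, and the 8-week stable-dose period has no single anchor

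*Protocol*

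**What the plan says.** **Platelet condition**

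- Protocol Section 1.7 covers all parts. It allows ruxolitinib up to 25 mg BID at platelets of 100 × 10^9/L or more, and for the band from 50 to <100 the dose "may not exceed 10 mg BID for subjects with platelet count" in that range.
- Inclusion criterion 3 (Section 3.2, repeated in the synopsis) reads "acceptable doses are 5 mg BID to 25 mg BID", for everyone.
- Section 5.3.2.1 repeats "Acceptable doses are 5 mg BID to 25 mg BID". The synopsis dosing entry and SAP Section 3 give the same range. Section 5.2.2 refers only to a stable dose. None has a platelet condition.
- Exclusion 4a (Section 3.3) is the only platelet limit in the eligibility criteria. It applies to counts below 50 × 10^9/L "in the 4 weeks before screening or platelet transfusion(s) within 8 weeks before screening".
- The ceiling does recur in the footnote to Table 2 (also in the synopsis and SAP Table 1), judged on the baseline platelet count. That table describes the Part 1 cohorts, and Part 1 is complete.

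**Stable-dose period**

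- Section 1.7: "All parts of the study require that subjects be on a stable dose of ruxolitinib for at least 8 weeks before the screening visit".
- Section 4.1: "including ruxolitinib administration at a stable dose for at least 8 weeks before randomization".
- Section 3.1: "with a stable ruxolitinib dose regimen for at least 8 weeks before the first administration of INCB050465". The synopsis study population and the Table 2 footnote use the same anchor.
- Criterion 3 requires 8 stable weeks and names no anchor.

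**The concern.** Section 1.7 offers these two conditions as part of the safety case for adding INCB050465 to ruxolitinib: it argues that a stable dose points to adequate tolerability. The text that decides who enters Parts 2 to 4 does not carry the first condition and leaves the second open to more than one reading. Section 3 allows no eligibility deviations, and neither Section 3 nor Section 5.3.2 refers the site back to Section 1.7.

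Two things are at stake. First, the protocol itself describes ruxolitinib thrombocytopenia as dose-related (Sections 1.6.1.2 and 1.8.5). A subject entering above the Section 1.7 ceiling may be more likely to reach a platelet count that can trigger interruption of INCB050465 before the Week 12 scan. Second, inadequate response is established by palpation at screening under criterion 4, so a late anchor allows that judgement to follow a recent ruxolitinib dose change.

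The SAP (Section 10.2.3) records that enrolment ended early. The conflict still decides which enrolled subjects belong in the eligibility-deviation listing (Listing 2.1.2).

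**Working it through.** The plan states no figure on this point to reproduce. The check compares passages and counts days.

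**1. Platelet condition: a test subject.** Take platelets of 60 × 10^9/L throughout, a stable 25 mg BID, and all other criteria met.

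| Text | Rule | Result |
|---|---|---|
| Criterion 3 | 5 to 25 mg BID | 25 is within range: passes |
| Exclusion 4a | excluded if below 50 | 60 is not below 50: passes |
| Section 5.3.2.1 | 5 to 25 mg BID | passes |
| Section 1.7 | at most 10 mg BID at 50 to <100 | 25 > 10: not allowed |

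Ratio to the ceiling: 25/10 = 2.5, the largest the range permits. At 15 and 20 mg BID it is 15/10 = 1.5 and 20/10 = 2.0.

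**2. Stable-dose anchor: days.** Inputs:

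- stable period: 8 × 7 = 56 days;
- screening visit between Day -35 and Day -8 (Section 6.1);
- Day -d lies d days before Day 1 (SAP Section 4.1.3), so d runs from 8 to 35;
- treatment starts within 3 days of randomization (Section 6.1).

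| Anchor | Minimum stable days before Day 1 | Minimum stable days before screening |
|---|---|---|
| Screening visit | 56 + d: 64 (d = 8) to 91 (d = 35) | 56 |
| First INCB050465 dose | 56 | 56 - d: 48 (d = 8) to 21 (d = 35) |

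The screening and first-dose anchors differ by d, that is 8 to 35 days. Randomization precedes first dose by at most 3 days, so that anchor requires 56 to 59 days before Day 1 and is close to the first-dose anchor.

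**3. On-study rules at 50 to <100 × 10^9/L.** Table 5 interrupts INCB050465 at 50 to <75 when this is a worsening of grade and not due to underlying disease, and below 50 whatever the baseline grade. Table 7 begins ruxolitinib action below 50, after more than 14 days off INCB050465 or earlier if the investigator judges it necessary. Section 5.3.2.1 says ruxolitinib may need reduction or interruption as platelets fall and refers to Section 5.5. No on-study ruxolitinib rule uses the 50 to <100 band of Section 1.7.

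**The case against.** The best defence is that a general range is not permission to exceed a specific limit. Table 2 prints the same 5 to 25 mg BID and then qualifies it by platelet count, so the protocol itself uses the range as an outer bound. Section 1.7 is current, mandatory in wording and covers all parts, so a site that follows the whole protocol has been told the limit. Other controls exist: Table 5, the ruxolitinib provisions of Section 5.3.2.1 and Table 7, twice-monthly hematology in Parts 2 to 4 (Section 1.8.6), and exclusion 19, which lets the investigator exclude a subject at significant risk.

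Much of this stands. The consequence is that a site can enrol such a subject, not that sites do, and the risk is partly mitigated. It does not remove the contradiction. In Table 2 the qualification sits beside the range. For Parts 2 to 4 it sits only in a justification section to which the criteria do not refer.

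Four stronger readings are tempting but unsupported:

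- A reader might infer that the criteria do not enforce a stable dose at all. Criterion 3 does require 8 stable weeks, and Section 5.3.2.1 ties dosing to the stable dose at screening. Only the anchor is missing.
- A reader might count three materially different anchors. Randomization and first dose are at most 3 days apart, so in effect there are two.
- A reader might take 21 days as the usual case. It needs screening on Day -35; with screening on Day -8 the figure is 48 days. All subjects also need at least 6 months of prior ruxolitinib.
- A reader might infer that interruptions will follow and distort the Week 12 comparison. The documents do not quantify this, and the eligibility text is the same for TG5D and TG5I/M, so no bias between groups is shown.

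**Conclusion.** The point holds as an internal contradiction in a safety-related eligibility rule, and it should be fixed. In Parts 2 to 4 a subject with platelets of 50 to <100 × 10^9/L can meet every criterion in Section 3 on up to 25 mg BID, while Section 1.7 limits that subject to 10 mg BID. The factor of 2.5 is a theoretical maximum. The documents do not say how many subjects fall in that platelet band or what dose they take.

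The stability requirement exists but is not anchored in criterion 3. Screening and first-dose anchors differ by 8 to 35 days, assuming screening falls within Day -35 to Day -8. Under the first-dose anchor the guaranteed stable time before the screening palpation is 21 to 48 days, against 56 under Section 1.7.

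No sample size, power, significance level, endpoint or planned analysis changes, so this does not rank among the most serious faults.

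**What to change.** Reconcile Section 1.7 with inclusion criterion 3 and its synopsis copy, the synopsis dosing entry, Sections 5.2.2 and 5.3.2.1, and SAP Section 3. There are two ways:

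- state the platelet condition in the operative eligibility and dosing text, with the time point at which platelets are judged; or
- no longer state it in Section 1.7 as applying to all parts.

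If the condition is kept, say whether it also applies when platelets fall on study. Separately, choose one anchor for the 8 stable weeks, write it into criterion 3, and align Sections 1.7, 3.1 and 4.1, the Table 2 footnote and the matching synopsis text. Which limit and which anchor apply is for the sponsor to decide.

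The cost is small: wording in several places and an added eligibility check. Platelet counts and ruxolitinib history are already collected. A few subjects may become ineligible; for those already enrolled, the settled rule determines whether they are listed as eligibility deviations.

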### **3.3. Subject Exclusion Criteria**

A subject who meets any of the following criteria will be excluded from the study:

1. Use of experimental drug therapy for MF or any other standard drug (eg, danazol, hydroxyurea, etc.), with the exception of ruxolitinib within 6 months of starting study (combination) therapy and/or lack of recovery from all toxicities from previous therapy (except ruxolitinib) to Grade 1 or better.
2. Inability to swallow food or any condition of the upper gastrointestinal tract that precludes administration of oral medications.
3. Unwillingness to be transfused with blood components.
4. Recent history of inadequate bone marrow reserve as demonstrated by the following:
  - a. Platelet count  $< 50 \times 10^9/\text{L}$  in the 4 weeks before screening or platelet transfusion(s) within 8 weeks before screening.
  - b. Absolute neutrophil count (ANC) levels  $< 0.5 \times 10^9/\text{L}$  in the 4 weeks before screening.
  - c. Subjects with peripheral blood blast count of  $> 10\%$  at the screening or baseline hematology assessments.
  - d. Subjects who are not willing to receive RBC transfusions to treat low hemoglobin levels.
5. Inadequate liver function at screening visit as demonstrated by the following:
  - a. Direct bilirubin  $\geq 2.0 \times$  the upper limit of laboratory normal (ULN). (NOTE: direct bilirubin will only be determined if total bilirubin is  $\geq 2.0 \times$  ULN).
  - b. ALT or AST  $> 2.5 \times$  ULN.
6. Inadequate renal function at screening visit as demonstrated by creatinine clearance  $< 50 \text{ mL/min}$  measured or calculated by Cockcroft-Gault equation, or glomerular filtration rate  $< 50 \text{ mL/min}/1.73 \text{ m}^2$  as calculated using the Modification of Diet in Renal Disease formula.
7. Active bacterial, fungal, parasitic, or viral infection that requires therapy. Subjects with acute infections requiring treatment should delay screening/enrollment until the course of therapy has been completed and the event is considered resolved. Prophylactic antibiotics will be permitted.
8. Active hepatitis B virus (HBV) or hepatitis C virus (HCV) infection that requires treatment or at risk for HBV reactivation. Hepatitis B virus DNA and HCV RNA must be undetectable upon testing. At risk for HBV reactivation is defined as hepatitis B surface antigen positive or anti-hepatitis B core antibody positive. Cytomegalovirus must be undetectable by polymerase chain reaction.

9. Known human immunodeficiency virus (HIV) infection.
10. Uncontrolled, severe, or unstable cardiac disease that in the investigator's opinion may jeopardize the safety of the subject or the compliance with the Protocol.
11. Active invasive malignancy over the previous 2 years except treated basal or squamous carcinomas of the skin, completely resected intraepithelial carcinoma of the cervix, and completely resected papillary thyroid and follicular thyroid cancers. Subjects with malignancies with indolent behavior such as prostate cancer treated with radiation or surgery may be enrolled as long as they have a reasonable expectation to have been cured with the treatment modality received.
12. Splenic irradiation within 6 months before receiving the first dose of INCB050465.
13. Concurrent use of any prohibited medications (see Section [5.7.4](#) for specific prohibited medications and the associated timeframe over which they are prohibited).
14. Active alcohol or drug addiction that would interfere with their ability to comply with the study requirements.
15. Prior therapy with any drug that inhibits PI3K (examples of drugs targeting this pathway include but are not limited to INCB040093, idelalisib, duvelisib, and TGR-1202).
16. Use of any potent CYP3A4 inhibitors or inducers ([Appendix B](#)) within 14 days or 5 half-lives (whichever is longer) before the first dose of INCB050465 or anticipated during the study.
17. Inadequate recovery from toxicity and/or complications from a major surgery before starting therapy.
18. Currently breastfeeding or pregnant.
19. Any condition that would, in the investigator's judgment, interfere with full participation in the study, including administration of study drug and attending required study visits; pose a significant risk to the subject; or interfere with interpretation of study data.
20. Inability to comprehend or unwilling to sign the informed consent form (ICF).
21. History of Grade 3 or 4 immune-related AEs from prior immunotherapy.
  - a. Any immune-related AEs of Grade 1 or 2 must be resolved before receiving the first dose of INCB050465.
22. History of immune-related ocular AEs of any toxicity grade.
23. Receipt of any live vaccine within 30 days of first dose of INCB050465.

